8.2.3.3 Analyses methods for safety endpoints

The safety analyses will be presented overall and by period as defined below:

- The baseline (BL) period will include all information recorded up to the randomization date.
- The radiation therapy (RT) or chemo/radiation period (RT&TMZ) will start on the day the radiation therapy is first given and end the day of the last administration of radiation therapy treatment plus 28 days.
- The adjuvant chemotherapy period (RT+TMZ) will start 29 days after the last dose of radiation therapy treatment and end-up 27 days after the first day of administration of the last cycle of adjuvant chemotherapy.
- The follow-up period (FUP) will start 29 days after the last dose of radiation therapy treatment or 28 days after the first day of administration of the last cycle of adjuvant chemotherapy.

The safety assessments include hematological toxicity, laboratory measurements and adverse events. Only the safety assessments performed before progression or within 7 days of progression and before start of any further anti-cancer therapy will be included in the analysis.

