5.5.3.2 Dose modification of temozolomide during the adjuvant treatment

During adjuvant treatment temozolomide dose interruptions as well as modifications are allowed.

Dose modifications are based on toxicity observed during prior treatment cycle. If multiple toxicities are seen, the dose administered should be based on the dose reduction required for the most severe grade of any single toxicity.

The possible doses of temozolomide are as follows:

Dose level	Dose mg/m ² /day (1-5)	Action
-1	100	Reduction if prior toxicity
0	150	Starting dose cycle 1
+1	200	Escalated dose as of cycle 2 in absence of toxicity

The first cycle of temozolomide is administered at the dose of 150 mg/m² d1-5. The dose is escalated at 200 mg/m² /day as of cycle 2 in absence of toxicity.

- Dose reduction according to worst adverse drug reaction during previous cycle

Adverse drug reaction	Value	CTCAE grading Version 3.0	Action
Haematological			
ANC and Platelets	≥ 1.5 x 10 ⁹ /L	0-1	Escalation to Dose Level +1 (only at cycle 2) ☐ or continue at current dose
	≥ LLN	0	
ANC and Platelets	≥ 1 and < 1.5 x 10 ⁹ /L	2	Dose unchanged
	≥ 50 and <LLN	1-2	
ANC and/or Platelets	< 1 x 10 ⁹ /L	3-4	Reduce by 1 dose level
	< 50 x 10 ⁹ /L	3-4	
Non haematological toxicity			
Except fatigue, alopecia, nausea and vomiting*		0-2	Escalation to Dose Level +1 (only at cycle 2) ☐ or continue at current dose
Except fatigue, nausea and vomiting*		3	Reduce by 1 dose level
Except fatigue, nausea and vomiting*		4	Stop treatment

☐ the dose of temozolomide may only be increased from 150 mg/m²/day to 200 mg/m²/day as of cycle 2.

* For nausea and vomiting, please see section 5.6.

A **maximum of 2 dose reductions** is permitted. However, if the same (in nature and severity) non haematological toxicity occurs at 2 subsequent cycles despite 1 dose reduction, a second dose reduction is not permitted and the patient should stop the treatment. **No dose reductions below 100 mg/m² are**

allowed, if 100mg/m² is not tolerated the patient should stop treatment. Once a dose has been reduced, **no dose re-escalation** is allowed.

- Treatment delay according to worst adverse drug reaction during previous cycle

Adverse Drug Reaction	Value	CTCAE Grading Version 3.0	Action
Haematological			
ANC	< 1.5 x 10 ⁹ /L	2-3-4	Delay up to 2 weeks until resolution to at least grade 1. If unresolved then stop
and/or Platelets	< 75 x 10 ⁹ /L	2-3-4	
Non haematological toxicity			

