6.3.1.3 Evaluation 4 weeks after the end of radiotherapy

- Physical examination including vital signs, and neurological evaluation
- Corticosteroid intake
- MMSE
- Quality of Life C30 and BCM20
- WHO-ECOG performance status
- Toxicity according to CTCAE v.3
- Complete blood count, all serum chemistries
- Gd-enhanced MRI or contrast CT scan of the brain
- Corticosteroid intake

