6.4 After the end of radiotherapy

Patients are followed every six months for disease assessment; in addition patients randomized to receive adjuvant temozolomide are followed every four weeks prior to the start of the next cycle of temozolomide.

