16.6 Reporting procedure for investigators

This procedure applies to all Serious Adverse Events (SAE) occurring from the time a subject is randomization until 30 days after last protocol treatment and to any SAE that occurs outside of the SAE detection period (after the 30-days period), if it is considered to be likely related to the investigational product or study participation.

Randomization till 30 days after last protocol treatment:	All SAEs
From day 31 after last protocol treatment:	Only related SAEs

All reporting must be done by the principle investigator or authorized staff member (i.e. on the signature list) to confirm the accuracy of the report.

All SAE data must be collected on the study-specific SAE form.

All SAEs must be reported immediately and no later than 24 hours from the time the investigator or staff became aware of the event.

All SAE-related information needs to be provided in English.

All additional documents in local language must be accompanied by a translation in English, or the relevant information must be summarized in a follow-up SAE report form.

Investigators participating through **EORTC** must fax/e-mail all SAE-related information to:

EORTC Pharmacovigilance:

[contact]

E-mail: [contact]

Investigators participating through **non-EORTC groups** should consult their **group specific appendix** for further details on the reporting of Serious Adverse Events.

To enable the EORTC to comply with regulatory reporting requirements, all initial SAE reports should always include the following minimal information: an identifiable patient (SeqID), a suspect medicinal product if applicable, an identifiable reporting source, the description of the medical event and seriousness criteria, as well as the causality assessment by the investigator. Complete information requested on the SAE form of any reported serious adverse event must be returned within 7 calendar days of the initial report. If the completed form is not received within this deadline, the EORTC Pharmacovigilance will make a written request to the investigator.

Queries sent out by the EORTC Pharmacovigilance need to be answered within 7 calendar days.

All forms need to be dated and signed by the principle investigator or any authorized staff member (i.e. on the signature list).

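### The safety periods in 8.2.3.3 use calendar cut-offs that do not match when toxicity is assessed or when adjuvant temozolomide is given, so findings can land in the wrong period, selectively and differently by arm

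*Combined protocol and SAP*

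**What the plan says.** **Period definitions (8.2.3.3).** Safety is presented overall and by period.

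- The RT or RT&TMZ period is to "end the day of the last administration of radiation therapy treatment plus 28 days".
- The adjuvant period "will start 29 days after the last dose of radiation therapy treatment" and will "end-up 27 days after the first day of administration of the last cycle of adjuvant chemotherapy".
- Follow-up starts either 29 days after the last radiotherapy dose or "28 days after the first day of administration of the last cycle of adjuvant chemotherapy".

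**When toxicity is assessed.**

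- A cycle lasts 28 days, with dosing on days 1-5 and at most 12 cycles (5.2.2.4).
- Under 6.4, "patients randomized to receive adjuvant temozolomide are followed every four weeks prior to the start of the next cycle of temozolomide". Section 6.4.2.1 lists toxicity, blood count and chemistry for that visit. Neither section gives a day or a window.
- A day-21 blood count, without chemistry, is required only in cycle 1, in cycle 2 after escalation, or after significant haematological toxicity in the previous cycle (6.4.2.2).
- For several toxicities the action in 5.5.3.2 is "Delay up to 2 weeks until resolution to at least grade 1. If unresolved then stop". Grade 4 non-haematological toxicity, with listed exceptions, stops treatment.
- Section 6.3.1.3 sets an "Evaluation 4 weeks after the end of radiotherapy", again without a window for toxicity or laboratory tests.

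**Related rules.** SAEs are collected "until 30 days after last protocol treatment" (16.6). The worst-value and worst-grade tables (8.2.3.3.1 to 8.2.3.3.4) cover a whole treatment period that is not defined. Section 7.5.2 assesses nadirs and acute non-haematological effects per cycle. No section says whether a record enters a period by onset date, assessment date or cycle.

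**The concern.** The adjuvant cut-off is tied to the last cycle, and which cycle is last can depend on what the closing visit shows. A cut-off placed just before that visit's nominal date therefore sorts findings by their consequence. The same result on the same cycle day is adjuvant toxicity if the patient goes on, and a follow-up finding if the patient stops.

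The start of the adjuvant period has a separate fault. It is fixed by the end of radiotherapy, not by the first adjuvant dose, so findings made before any adjuvant temozolomide can be labelled adjuvant. This can happen only in arms 3-4.

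Safety is a secondary objective (2.2). Because 8.2.3.3.4 rules out formal comparison, the descriptive tables carry the whole safety message. A by-period table that understates treatment-ending toxicity, or labels the same visit differently by arm, would mislead readers about what adjuvant temozolomide adds.

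**Working it through.** **1. The plan's own cut-off.** Count the first dosing day of a cycle as day 1.

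- Adjuvant period ends: 1 + 27 = day 28.
- Follow-up starts: 1 + 28 = day 29.
- The periods join without gap or overlap.
- Next cycle due after a 28-day cycle: 1 + 28 = day 29.
- Latest point of the permitted 2-week delay: 29 + 14 = day 43.

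**2. Where the closing assessment falls, if filed by date.**

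| Assessment of the last cycle | Period |
|---|---|
| Day 28 or earlier | Adjuvant |
| Day 29 (due date of next cycle) | Follow-up |
| Days 30-43 (during a delay) | Follow-up |

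**3. Why the shift is selective.** Let cycle k start on date S(k), let L be the last cycle, and let the period end at E = S(L) + 27. Take a finding dated S(k) + 28 + d, with d from 0 to 14 days of delay.

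- Treatment stops, so k = L: E = S(k) + 27, and the finding is at least one day after E. It goes to follow-up.
- Treatment continues, so L is at least k + 1 and S(L) is at least S(k) + 28 + d: E is at least S(k) + 55 + d (28 + 27 = 55). The finding is inside the adjuvant period.

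**4. Which data are most exposed.** Laboratory values carry a sample date and no onset date. From cycle 3 the sample before the next cycle is usually the only scheduled laboratory check of a cycle. For chemistry this is so in every cycle, because the day-21 test is a blood count only.

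**5. The radiotherapy boundary.** Count the last radiotherapy day as day 0.

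| Post-radiotherapy visit | Arms 1-2 | Arms 3-4 |
|---|---|---|
| +28 days (nominal 4 weeks) or earlier | RT period | RT period |
| +29 days or later | Follow-up | Adjuvant, even before any adjuvant dose |

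For arm 1 this visit holds the only scheduled blood test after baseline. Tests during radiotherapy are for temozolomide patients only (6.3.1.1, 6.3.1.2), and the six-monthly visits have none (6.4.1).

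**6. Patients in arms 3-4 never given adjuvant temozolomide.** Their adjuvant period has a start (+29 days) but no last cycle from which to compute its end. Section 8.1.1 expects 10% of patients to fail during radiotherapy or in the month after it. With 748 randomized and equal allocation assumed, arms 3-4 hold 748 / 2 = 374 patients, and 0.10 x 374 is about 37. This is a planning figure. Those who fail by progression would add few records, because 8.2.3.3 excludes assessments more than 7 days after progression.

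**7. Against the SAE window.** After a last dose on day 5, SAE collection runs to 5 + 30 = day 35, so 35 - 28 = 7 days of it lie in follow-up. After radiotherapy the difference is 30 - 28 = 2 days.

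**The case against.** The strongest reply is that the cut-offs do harm only under assumptions the plan does not make. Much of it stands.

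- **The visit is not fixed at day 29.** It must only precede the next cycle, so day 28 or earlier complies and is inside the period. After cycle 12 there is no next cycle and no such visit. A reader might infer that every patient treated on schedule is misfiled; the documents do not support that.
- **Filing by date is not stated.** The wording in 8.2.3.3 about assessments performed sets the progression and further-therapy limit; it does not assign records to periods. Sections 7.5.2 and 8.2.6 work by cycle. Adverse events filed by onset or by cycle would stay in the adjuvant period if they arose on days 1-28. So one cannot say that grade 4 events are always filed as follow-up. This reply is weaker for laboratory values, and 8.2.3.3 does not link its calendar periods to cycles.
- **Nothing is shown to be lost.** An overall presentation is planned, and follow-up is itself a reported period. A reader might infer that the findings disappear from the worst-grade tables. That holds only if the whole treatment period excludes follow-up, which the plan does not say.
- **The nominal post-radiotherapy visit is safe.** At +28 days it is inside the RT period; only a late visit crosses.
- **Repeat haematological toxicity has some cover**, because the day-21 count is then required.
- **The SAE window serves reporting**, so a different length is not in itself a contradiction.
- **Undosed patients in arms 3-4** could be placed in follow-up through its alternative start at +29 days. The text does not say that this branch applies to them.

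What remains is a stated rule, not only missing detail. Its end point depends on whether treatment stopped, and its start point ignores whether adjuvant treatment began.

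**Conclusion.** The point holds as one of misclassification between safety periods. Dated results from a last cycle, taken on day 29 or during the permitted delay, go to follow-up, whereas the same results stay in the adjuvant period when treatment continues. A post-radiotherapy visit after +28 days is labelled adjuvant in arms 3-4 and follow-up in arms 1-2. Undosed patients in arms 3-4 have an adjuvant period with no defined end.

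The direction of the first effect is clear: it understates treatment-ending findings in the adjuvant table. Its size cannot be derived, because the documents give no distribution of visit days, no rate of findings first seen at the closing visit, and no probability that such a finding stops treatment. The conclusion assumes filing by assessment date, which is natural for laboratory values and open for adverse events. No significance test is affected. This is a cheap improvement worth making, not a threat to the primary analysis.

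**What to change.** Rewrite the period definitions in 8.2.3.3:

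1. **RT or RT&TMZ period, all arms:** from the first radiotherapy day through the 4-week post-radiotherapy evaluation, ending before the first adjuvant dose.
2. **Adjuvant period:** from the first adjuvant dose to the later of 30 days after the last temozolomide dose (which matches 16.6) and the evaluation that closes the last cycle. After cycle 12, where no pre-cycle visit is scheduled, the 30-day limit applies unless a closing evaluation was done later. Patients never given adjuvant temozolomide have no adjuvant period.
3. **Assignment rule:** adverse events by onset date, and each pre-cycle laboratory value to the cycle it closes. This assumes that onset dates are on the case report forms, which are not part of the documents.
4. **Whole treatment period:** define it as the union of the periods in items 1 and 2.

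The cost is SAP wording and programming. No new data are needed; Appendix M states that all patients have completed study treatment. The downside is that period lengths will vary by a few days between patients. Any by-period table already released for the adjuvant question should state which definitions it used.

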8.2.2 Analysis populations

- Intention-to-treat population: All randomized patients will be analyzed in the arm they were allocated by randomization.
- Per protocol population: All patients who are eligible (including 1p/19q LOH status at central review) and have started their allocated treatment (i.e. RT started in all arms).
- Safety population: All patients who have started their allocated treatment (i.e. RT started in all arms). The safety of patients excluded from the safety population is separately reported.

A patient will be considered to be eligible if he/she did not have any major deviations from the patient entry criteria listed in chapter 3 of the protocol. Eligibility will be assessed by the Study Coordinator based on the review of each patient file.

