8.2.3 Statistical methods

8.2.3.1 Analyses populations

All the analyses of the efficacy endpoints (overall survival and progression-free survival) will be performed in the intention-to-treat population.

All the analyses of the safety endpoints will be performed in the safety population.

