8.2.3.3.1 Hematological parameters

For the whole treatment period, the worst value of each hematological parameter will be calculated for each patient. The worst value of each parameter will then be coded and the frequency of each category will be tabulated. A table with grade 3 or 4 rates will be provided.

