8.2.3.3.4 Related AEs

The worst grade of each AE item will be calculated as the maximum grade reported **as likely related** for that item over the whole treatment period. The frequency of the worst grade of each AE item will be tabulated. A table with grade 3 or 4 rates will be provided.

There will be no formal comparison of safety endpoints. No p-value will be carried out.

Baseline AE grades will not be accounted for in any AE analyses.

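### The cut at progression + 7 days removes some on-treatment adjuvant toxicity from the safety tables, and adjuvant-period rates count patients who never started adjuvant temozolomide

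*Combined protocol and SAP*

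**What the plan says.** Section 8.2.3.3 sets the rule for every safety table: "Only the safety assessments performed before progression or within 7 days of progression and before start of any further anti-cancer therapy will be included". Section 8.2.3.3 also says "The safety analyses will be presented overall and by period as defined below". The radiotherapy period is to "end the day of the last administration of radiation therapy treatment plus 28 days", and the adjuvant period is to "end-up 27 days after the first day of administration of the last cycle of adjuvant chemotherapy". Neither period end depends on progression.

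Sections 8.2.3.3.1 to 8.2.3.3.4 take the worst value or grade over the whole treatment period, and each promises that "A table with grade 3 or 4 rates will be provided". Section 8.2.3.3.4 adds: "There will be no formal comparison of safety endpoints".

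On the denominator, 8.2.3.1 says "All the analyses of the safety endpoints will be performed in the safety population", and 8.2.2 defines "Safety population: All patients who have started their allocated treatment", explained there as radiotherapy started in all arms.

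Three sections govern treatment around progression:
- 5.3 ends treatment at documented progression.
- 7.1.2 warns about pseudo-progression, allows adjuvant treatment to be stopped within 3 months of radiotherapy only exceptionally, and dates confirmed progression back to the first increase.
- 7.1.2.1 has adjuvant treatment continue when there is only radiological progression before cycle 1, with such cases to be reviewed.

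**The concern.** The cut is tied to the progression date, while exposure to the drug is not always tied to it. A patient in arm 3 or 4 can receive protocol temozolomide after the date that is eventually recorded as progression. Toxicity from those cycles lies inside the adjuvant period that 8.2.3.3 itself defines, and inside the whole treatment period over which worst grades are taken, yet the cut removes it. Sections 7.5.2 and 8.2.6 also call for a nadir in each cycle and across all cycles, which cannot be met for a cycle that falls after the cut.

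The safety of adjuvant temozolomide is a secondary objective (2.2), and the adjuvant-phase loss arises only in the two arms whose adjuvant toxicity is being described.

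A second, separate issue concerns the by-period tables. The stated population includes patients who never began adjuvant treatment, so an adjuvant-period rate is diluted as a description of patients who took the drug.

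**Working it through.** There is no figure in the plan to reproduce, because the point concerns an inclusion rule. The check is day arithmetic on the plan's own schedule.

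**Inputs.** Cut: progression date + 7 days (8.2.3.3). Cycle: 28 days, with dosing on days 1 to 5 (5.2.2.4). Adjuvant period: from day 29 after the last radiotherapy dose to 27 days after day 1 of the last cycle (8.2.3.3). Scan 4 weeks after radiotherapy (6.3.1.3). Blood counts before each cycle (6.4.2.1), and on day 21 of cycle 1, of cycle 2 if the dose is escalated, or after significant hematological toxicity (6.4.2.2).

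**(a) Progression on day d of the last cycle.**
- Days up to d + 7 are kept. Days dropped = 28 − (d + 7) = 21 − d, with a floor of 0.
- d = 1: 20 days dropped. d = 21 or later: none.
- If d is uniform on 1 to 28, the mean is (20 + 19 + … + 1)/28 = 210/28 = 7.5 days. This assumes that no further therapy starts earlier.
- A nominal day-21 count, where scheduled, is dropped when 21 > d + 7, that is, when d is 13 or less.
- The earliest possible cut is day 1 + 7 = day 8, after dosing ends on day 5. The dropped days are therefore post-dose days within the cycle.

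**(b) Back-dated progression (assumed example).** Day 0 is the last radiotherapy dose, with no cycle delays. Cycles start on days 29, 57 and 85.
- First increase on the 4-week scan: day 28. Cut: 28 + 7 = day 35.
- Cycle 1 day 21 = 29 + 20 = day 49. Cycle 2 day 21 = 57 + 20 = day 77.
- If recognised as true progression at day 91: 91 − 35 = 56 days are excluded up to recognition, and three cycles have started. The assessments on days 49, 57, 85 and, if the dose was escalated, 77 are dropped.
- If recognised at week 8 (day 56): 56 − 35 = 21 days are excluded, one cycle has started, and the day-49 count is dropped.
- The 4-week and pre-cycle-1 assessments are kept in both cases, as are arm 4's weekly counts during radiotherapy.

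**(c) Direction.** Removing assessments cannot raise a patient's worst grade. With the safety population fixed as denominator, the proportion with a worst grade of 3 or higher can only fall or stay the same. Frequencies of lower grades can rise.

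**(d) Denominator.** Under 8.2.3.3 a patient with no adjuvant cycle passes directly to follow-up and contributes no adjuvant-period event. Rate in the safety population = rate among starters × (1 − share not starting). With an assumed 10% rate among starters:

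| Share not starting (assumed) | Rate shown |
|---|---|
| 5% | 10% × 0.95 = 9.5% |
| 10% | 10% × 0.90 = 9.0% |
| 20% | 10% × 0.80 = 8.0% |

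The middle row is guided by 8.1.1, which expects 10% of patients to fail during radiotherapy or within a month of it. That is not the same quantity as not starting adjuvant treatment.

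**The case against.** The cut has a fair purpose: it keeps events caused by the tumor out of the toxicity tables, in line with the convention in 16.2 for serious events. Exposure after progression should be uncommon, because 5.3 stops treatment at documented progression. If the caution in 7.1.2 or the case review in 7.1.2.1 means that a change is never labelled progression, nothing is cut. Tables based on worst grade keep any earlier grade 3 or 4 event. Serious events are collected to 30 days after the last treatment (16.6), and 12.1.2 promises summary statistics of all data collected. No formal safety comparison is planned. The change would also come late: the monitoring committee has already recommended release of the adjuvant comparison (8.3.2), and all patients have finished treatment (Appendix M).

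All of this stands as a limit on the size of the problem. None of it returns the excluded assessments to the planned tables: 16.6 governs reporting, and 12.1.2 is a general clause that does not override the cut in 8.2.3.3.

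A reader might infer that the plan leaves the by-period denominator unstated. It does not: 8.2.3.1 covers all safety analyses, so read literally the safety population applies to every period. A reader might also infer that the cut could bias rates in either direction. That would need a denominator of patients with an included assessment, which no section proposes.

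**Conclusion.** The point holds as a minor one. The cut has no on-treatment exception, and 7.1.2 and 7.1.2.1 allow adjuvant cycles in arms 3 and 4 to fall after the recorded progression date. Toxicity from those cycles is lost to the tables, in one direction only for grade 3 or worse. The number of patients affected cannot be derived from the documents, and the overall effect is probably small. The timing examples assume no cycle delays, and the recognition dates in (b) are assumptions that match no scheduled scan. The denominator issue is one of usefulness: the plan states a denominator, but it is not the one that describes patients exposed to adjuvant drug.

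It would be tempting to conclude that a large part of adjuvant exposure could vanish from the tables. The documents do not support that, because it would need many further cycles after the first increase, against the general rule in 5.3.

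**What to change.** In 8.2.3.3, keep the present display and add:

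> A parallel on-treatment display will include all safety assessments from first protocol treatment to the last RT day + 28 days or, if adjuvant temozolomide was given, 27 days after day 1 of the last adjuvant cycle, before any further anti-cancer therapy and regardless of progression. Adjuvant-period rates in arms 3 and 4 will also be shown with safety-population patients who started adjuvant temozolomide as denominator; baseline, RT and follow-up tables keep the safety population. The number of patients given protocol temozolomide after their progression date will be reported by arm.

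These are the period ends already in 8.2.3.3, so no new window is introduced. Sections 5.3, 7.1.2, 7.1.2.1 and 8.2.3.3 must be reconciled on what happens around progression; no treatment rule is proposed here.

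The cost is extra programming. Some disease-related events will enter the added display, which is why the existing one stays beside it. Only data already collected can be used. Assessments before each dosed cycle should exist (6.4.2.1), but other non-serious toxicity after progression may be incomplete, because 6.5 lists no toxicity assessment.
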